6.4.2 Response Assessment

CBR is defined as the number of patients with CR, partial response (PR) or stable disease (SD) (for at least 12 weeks) divided by the number of patients in the analysis set. Tumor response

will be defined as best response, based on local investigator's assessment according to RECIST criteria guidelines (version 1.1).

ORR is defined as the proportion of the subjects in the analysis set who have a CR or PR based on RECIST v.1.1:

- **CR**: Complete disappearance of all target lesions. Any pathological lymph nodes (target or non-target) must have reduction in short axis to < 10 mm.
- **PR**: At least a 30% decrease in the sum of diameters of target lesions, taking as reference the baseline sum diameters.
- **SD**: Neither sufficient shrinkage to qualify for PR, nor sufficient increase to qualify for PD, taking as reference the smallest sum diameters while on study.
- **PD**: At least a 20% increase in the sum of diameters of target lesions, taking as reference the smallest sum diameters while on study. The development of new, previously undetected lesions is also considered progression.

DoR is defined as the time from first documented CR or PR until disease progression or death from any cause, based on local investigator's assessment according to RECIST criteria v.1.1. In case of the patient first reaching PR and later CR, the duration of CR will be measured and reported separately, starting from the date when first documented, and ending when a progressive disease is diagnosed, or the patient dies.

Maximum tumor shrinkage is defined as the percentage of tumor shrinkage from baseline (obtained from the sum of the largest diameters of the target lesions), based on local investigator's assessment according to RECIST criteria v.1.1.

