5.4.1 Response Efficacy Definitions

5.4.1.1 RECIST V.1.1

Overall response according RECIST v1.1 will be obtained from target lesion response, non-target lesion response and new lesions, as follows:

Target Lesions	Non-target Lesions	New Lesions	Overall Response
CR	CR	No	CR
CR	Non-CR/non-PD	No	PR
CR	Not all evaluated	No	PR
PR	Non-CR/Non-PD or not all evaluated	No	PR
SD	Non-CR/Non-PD or not all evaluated	No	SD
Not all evaluated	Non-PD	No	NE
PD	Any	Yes or No	PD
Any	PD	Yes or No	PD
Any	Any	Yes	PD

The following results will be reported in all patients and in patients with measurable disease.

- The unconfirmed Best Overall Response, defined as the best overall response recorded from the start of the study treatment until 35 days after last dose administration date and confirmation of response is not required.
 - o When CR or PR is the best response across all time points, then best overall response will be CR or PR respectively.
 - o When SD is the best response for ≥ 12 weeks the best overall response will be SD ≥ 12 w.
 - o When SD is the best response for < 12 weeks the best overall response will be SD < 12 w.
 - o When non-target disease only and Non-CR/Non-PD is the best response for ≥ 12 weeks the best overall response will be SD ≥ 12 w.
 - o When non-target disease only and Non-CR/Non-PD is the best response for < 12 weeks the best overall response will be SD < 12 w.
 - o When PD is the best response across all time points, best overall response will be PD.
 - o When there is no evaluable tumor assessments best overall response will be NE.
- The confirmed Best Overall Response, defined as the best overall response recorded from the start of the study treatment until 35 days after last dose administration date and confirmation of response is required.
 - o When CR or PR is the best response for ≥ 4 weeks then best overall response will be CR or PR respectively.
 - o When SD is the best response for ≥ 12 weeks the best overall response will be SD ≥ 12 w.
 - o When SD is the best response for < 12 weeks the best overall response will be SD < 12 w.
 - o When non-target disease only and Non-CR/Non-PD is the best response for ≥ 12 weeks the best overall response will be SD ≥ 12 w.
 - o When non-target disease only and Non-CR/Non-PD is the best response for < 12 weeks the best overall response will be SD < 12 w.
 - o When PD is the best response across all time points, best overall response will be PD.

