 - o When there is no evaluable tumor assessments best overall response will be NE.
- Unconfirmed Objective Response Rate (ORR) is defined as the proportion of patients with best overall response of unconfirmed CR or unconfirmed PR.
- Unconfirmed Clinical Benefit Rate (CBR) is defined as the proportion of patients with best overall response of unconfirmed CR or unconfirmed PR or SD ≥ 12 w.
- Confirmed Objective Response Rate (ORR) is defined as the proportion of patients with best overall response of confirmed CR or confirmed PR.
- Confirmed Clinical Benefit Rate (CBR) is defined as the proportion of patients with best overall response of confirmed CR or confirmed PR or SD ≥ 12 w.
- PFS is defined as the time from start dose until death by any cause or objective tumor progression according to RECIST v.1.1 or clinical disease progression. Patients with no progression or death will be censored at the date of their last evaluable imaging previous 35 days after last dose administration date. Censoring rules are specified below:

Situation	Date of progression or censoring	Outcome
Progression documented between scheduled visits	Earliest of: 
 • Date of assessment by investigator (if progression is based on clinical criteria); or • Date of assessment showing new lesion (if progression is based on new lesion); 	Progressed

Situation	Date of progression or censoring	Outcome
	or • Date of last radiological assessment of measured lesions (if progression is based on increase in sum of measured lesions).	
Death before first progression disease (PD) assessment	Date of death.	Progressed
Death between adequate assessment visits	Date of death.	Progressed
No progression	Date of last radiological assessment of measured lesions.	Censored
Treatment discontinuation for undocumented progression	Date of last radiological assessment of measured lesions.	Censored
Treatment discontinuation for toxicity or other reason	Date of last radiological assessment of measured lesions.	Censored

- 6-months PFS rate is defined as the proportion of patients who are alive and progression-free at 6 months from the date of first dose of study treatment based on RECIST criteria.
- The Overall Survival (OS) is defined as the time from start dose until death from any cause. Patients with no death will be censored on the last available follow-up date.

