- The duration of response (DoR) is defined as the time from start dose of first tumor response (either CR or PR) to disease progression or death due to any cause. The DoR will be calculated for the patients with unconfirmed CR or PR.
- The Time to Progression (TTP) is defined as the time from start dose to objective tumor progression or clinical disease progression (TTP does not include deaths). Patients with no progression will be censored at the date of their last evaluable imaging previous 35 days after last dose administration date.
- The Time to Response (TTR) is defined as the time from start dose to unconfirmed ORR date. Patients without ORR will be censored at the date of their last evaluable imaging previous 35 days after last dose administration date.
- Maximum Tumor Shrinkage (best percentage of change from baseline in the size of target tumor lesions) is defined as the biggest percentage of tumor shrinkage from baseline (obtained from the sum of the largest diameters of the target lesions).

5.4.1.2 irRECIST

The following results will be reported in all patients and in patients with measurable disease:

- The response assessment of the tumor is defined as best response according to:
 - irCR: complete disappearance of all measurable and non-measurable lesions. Lymph nodes must decrease to < 10 mm in short axis. Confirmation of response is not mandatory.
 - irPR: decrease of $\geq 30\%$ in Total Measured Tumor Burden (TMTB) relative to baseline, non-target lesions are irNN, and no unequivocal progression of new non-measurable lesions.
 - irSD: failure to meet criteria for irCR or irPR in the absence of irPD.
 - irNN: no target disease was identified at baseline and at follow-up the patient fails to meet criteria for irCR or irPD.
 - irPD: minimum 20% increase and minimum 5 mm absolute increase in TMTB compared to nadir, or irPD for non-target or new non-measurable lesions. Confirmation of progression is recommended minimum 4 weeks after the first irPD assessment.
 - irNE, used in exceptional cases where insufficient data exists.

- irORR is defined as the proportion of participants with irCR or irPR. Participants who do not have on-study radiographic tumor re-evaluation, who received anti-tumor treatment other than the study medication prior to reaching an irCR or irPR, or who died, progressed, or dropped out for any reason prior to reaching an irCR or irPR will be counted as non-responders in the assessment of irORR.

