Secondary 2	FAS set	BOR	
 - When CR or PR is the best response across all time points, then best overall response will be unconfirmed CR or unconfirmed PR respectively. - When CR or PR is the best response for ≥ 4 weeks then best overall response will be confirmed CR or confirmed PR respectively. - When SD is the best response for ≥ 24 weeks the best overall response will be SD ≥ 24 w. - When SD is the best response for < 24 weeks the best overall response will be SD < 24 w. - When non-target disease only and Non-CR/Non-PD is the best response for ≥ 24 weeks the best overall response will be SD ≥ 24 w. - When non-target disease only and Non-CR/Non-PD is the best response for < 24 weeks the best overall response will be SD < 24 w. - When PD is the best response across all time points, best overall response will be PD. - When there is no evaluable tumor assessments best overall response will be NE. 	The number and proportion of patients with response with the 95% Pearson-Clopper CI will be calculated.
Sensitivity to secondary 2	PP set	BOR	Same as above	Same as above
Secondary 3	FAS set	Confirmed ORR	
 - Patient with missing confirmed ORR outcomes will be considered as no responders. - Patients without any post-baseline assessment will be considered as non-responders. 	The number and proportion of patients with response with the 95% Pearson-Clopper CI will be calculated.

Estimand	Population	Variable	Intercurrent event strategy	Summary measure
Sensitivity to secondary 3	PP set	Confirmed ORR	Same as above	Same as above
Secondary 4	FAS set	Unconfirmed CBR	
 - Patient with missing Unconfirmed ORR outcome will be considered as no responders. - Patients without any post-baseline assessment will be considered as non-responders. 	The number and proportion of patients with response with the 95% Pearson-Clopper CI will be calculated.
Sensitivity to secondary 4	PP set	Unconfirmed CBR	Same as above	Same as above
Secondary 5	FAS set	Confirmed CBR	
 - Patient with missing confirmed ORR outcomes will be considered as no responders. - Patients without any post-baseline assessment will be considered as non-responders. 	The number and proportion of patients with response with the 95% Pearson-Clopper CI will be calculated.
Sensitivity to secondary 5	PP set	Confirmed CBR	Same as above	Same as above

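### Best overall response splits stable disease at 12 weeks in SAP 5.4.1.1 but at 24 weeks in Table 2, and irCBR sets no minimum duration, so neither lines up with CBR

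*SAP*

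**What the plan says.** **BOR, SAP 5.4.1.1.** For both unconfirmed and confirmed BOR, the cut is 12 weeks: "When SD is the best response for ≥ 12 weeks the best overall response will be SD ≥ 12 w". Patients with non-target disease only are treated alike: "When non-target disease only and Non-CR/Non-PD is the best response for ≥ 12 weeks the best overall response will be SD ≥ 12 w".

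**BOR, SAP Table 2, Secondary 2.** The same variable is cut at 24 weeks: "When SD is the best response for ≥ 24 weeks the best overall response will be SD ≥ 24 w", with the complement "When SD is the best response for < 24 weeks the best overall response will be SD < 24 w". The two lines for non-target-only disease also use 24 weeks, making four lines in all.

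**CBR.** SAP 5.4.1.1 defines unconfirmed CBR as the "proportion of patients with best overall response of unconfirmed CR or unconfirmed PR or SD ≥ 12 w"; confirmed CBR uses the same 12 weeks. Protocol 6.4.2 agrees, counting CR, "partial response (PR) or stable disease (SD) (for at least 12 weeks) divided by the number of patients in the analysis set". The CBR rows of Table 2 (Secondary 4 and 5) state no duration.

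**irCBR, SAP 5.4.1.2.** A patient counts with irCR, irPR or irSD. The component definitions are "irSD: failure to meet criteria for irCR or irPR in the absence of irPD" and "irNN: no target disease was identified at baseline and at follow-up the patient fails to meet criteria for irCR or irPD". Neither carries a duration, irNN is not named in irCBR, and the irCBR row of Table 2 adds only missing-data rules.

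**Declared changes.** SAP 5.7 lists the alpha notation and the replacement of time to progression by time to response. It mentions no change to the duration of stable disease.

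**The concern.** One variable has two definitions in one document, and CBR is defined through that variable. A programmer who follows Table 2 has no category for stable disease of at least 12 weeks. The BOR summary and the CBR rows of the same table would then not reconcile.

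irCBR has a related problem. Protocol 2.3.1 lists CBR as per irRECIST among the exploratory endpoints, and the protocol's only definition of CBR carries the 12-week minimum. The SAP drops that minimum for irCBR without comment. SAP 5.4.7 plans a comparison of RECIST with irRECIST. If CBR is set against irCBR there, part of any difference may come from the definitions and not from how the two criteria read the scans. The irCBR subgroup row in SAP Table 4 inherits the same definition.

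**Working it through.** The plan gives no figure of its own on this point, so the check sets the definitions side by side and then sizes the effect.

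**1. How each rule classifies a patient without CR or PR**

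| Patient | BOR, SAP 5.4.1.1 | BOR, Table 2 | CBR | irCBR (irSD or irNN, as applicable) |
|---|---|---|---|---|
| SD under 12 weeks | SD, lower category | SD, lower category | failure | success |
| SD 12 to under 24 weeks | SD, upper category | SD, lower category | success | success |
| SD 24 weeks or more | SD, upper category | SD, upper category | success | success |
| Non-target only, Non-CR/Non-PD, 12 weeks or more | SD, upper category | upper category only from 24 weeks | success | unclear |

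The second row shows why CBR cannot be rebuilt from the Table 2 BOR row. The first shows the duration gap between CBR and irCBR. SAP 5.4.1.2 fails only patients who progress, die, drop out or start other anti-tumour treatment before reaching irSD (or have no on-study scan), so one stable scan is enough. The last row is unclear because irNN is a separate category, yet the irSD wording, read literally, can also cover these patients. They can be enrolled, since protocol 4.2 (item 8) accepts evaluable disease.

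**2. Size per patient.** With N = 18 (SAP 1.6), one reclassified patient moves a rate by 1/18 = 5.6 points. With exact 95% Clopper-Pearson intervals, 6/18 = 33.3% (13.3 to 59.0) becomes 5/18 = 27.8% (9.7 to 53.5).

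**3. Illustration under assumed counts.** The documents do not give these numbers. Assume 3 responders, 1 patient with SD of 24 weeks or more, *b* with SD of 12 to under 24 weeks and *a* with SD under 12 weeks, no non-target-only patients, and the same readings under both criteria.

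- CR + PR + upper SD category from Table 2: (3 + 1)/18 = 22.2% (6.4 to 47.6), whatever *b* is.
- CBR: (3 + 1 + *b*)/18 = 22.2%, 27.8%, 33.3% or 44.4% for *b* = 0, 1, 2 or 4.
- irCBR with *b* = 2: (3 + 1 + 2 + *a*)/18 = 33.3%, 44.4% or 55.6% for *a* = 0, 2 or 4, against CBR of 33.3%.

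**4. Where the cuts fall on the scan schedule.** Protocol 6.4.1 sets scans every 8 weeks ± 7 days for the first 6 months. Counting from first dose:

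- week 8: 56 ± 7 = days 49 to 63
- week 16: 112 ± 7 = days 105 to 119
- week 24: 168 ± 7 = days 161 to 175

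Twelve weeks is day 84, which lies in no scheduled window. Twenty-four weeks is day 168, inside the week-24 window. Days 161 to 167, 7 of the 15 days, fall short of it. If one day is added, as in the SAP's irPFS formula, 6 of the 15 fall short. If duration runs to a scheduled scan, the scan date alone can therefore decide the Table 2 category. Unscheduled scans and clinical progression are left out of this step.

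**The case against.** The strongest case is that little depends on this. BOR is not among the secondary endpoints in SAP 3.2 or in protocol 2.2.1 and 8.4.2. CBR has an explicit 12-week rule in both documents, and the Table 2 CBR rows do not contradict it. SAP 5.4 calls all efficacy analysis exploratory. irCBR is exploratory too, no SAP sentence says it must mirror CBR, and SAP 5.4.7 names no CBR-versus-irCBR contrast.

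The duration gap also depends on a convention the SAP does not state. If SD runs from first dose to progression, a patient stable at week 8 who progresses at the week-16 scan has 105 to 119 days of SD and counts in CBR. The gap then narrows to patients who, after a stable week-8 scan, die, drop out, progress clinically or progress on an unscheduled scan before day 84. If SD runs to the last stable scan, the gap is wider. Reporting in patients with measurable disease, which SAP 5.4.1.1 and 5.4.1.2 already plan, removes the irNN question.

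Most of this stands as a limit on impact. It does not remove the contradiction: four consistent lines at 24 weeks are not a one-character slip, and SAP 5.7 declares no change. Nor is the irCBR point only a preference, because the endpoint is the protocol's CBR read by irRECIST and that CBR requires 12 weeks. The measurable-disease analysis leaves the duration difference in place.

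**Conclusion.** The concern holds. The Table 2 BOR row conflicts with SAP 5.4.1.1 and cannot be mapped to CBR. irCBR omits the 12-week minimum that CBR carries and leaves non-target-only patients undefined; on irNN the finding is ambiguity, not a demonstrated exclusion.

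The effect is confined to the BOR summary, exploratory irCBR with its subgroup row, and any CBR-versus-irCBR contrast within the RECIST/irRECIST comparison. The primary ORR analysis, sample size, alpha and power do not use the duration of stable disease. The size is 5.6 points per reclassified patient, small against the interval width. The number of patients affected cannot be predicted: it depends on progression times the documents do not give, on scan dates and on how SD duration is measured. The point should be settled before programming, so that no definition is chosen after open-label results are known.

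**What to change.** 1. In SAP Table 2, Secondary 2, change the four 24-week thresholds to 12 weeks, matching 5.4.1.1 and CBR.
2. In SAP 5.4.1.2, define irCBR as irCR, irPR, or irSD or irNN lasting at least 12 weeks.
3. State once how the duration of stable disease is measured (start date, end date and day count), and apply it to both CBR and irCBR.
4. If a 24-week BOR split, or an irCBR without a minimum duration, is intended, say so in the SAP with the reason.

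This costs SAP wording and programming, with no new data and no effect on patients. irCBR may come out lower, because irSD under 12 weeks would no longer count. Naming irNN could offset this by 5.6 points for each non-target-only patient stable for at least 12 weeks who would otherwise have been left out. The 12-week CBR definition does not change.

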3.2.4 Follow-up after treatment discontinuation

EoS will occur 12 months after the last patient has been enrolled in the study (treatment start).

Patients discontinuing the study treatment period will enter a post-treatment follow-up period during which survival and new anti-cancer therapy information will be collected every 3 months (\pm 14 days) from the last dose of investigational product until the end of study (EoS).

During this visit, status survival and post study anti-cancer therapy evaluation will be collected (telephone contact is acceptable).

LPLV: 12 months after first study dose of the last patient or progressive disease experienced in all patients or when the trial is terminated by the Sponsor, whichever is earlier.

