8.6 Missing Data Management

Study variables could be missing for patients who withdrawn from the trial or for specific visits. We will report reasons for withdrawal. Patient with missing in response outcomes (ORR and CBR) will be considered as no responders. Other outcomes will be managed with simple imputations methods. The effect that any missing data might have on results will be assessed via sensitivity analysis of study sets.

For PFS and DoR, patients without a date of disease progression or death will be analyzed as censored observations on the date of last tumor assessment. If no post-baseline tumor assessment is available, patients will be censored at the date of randomization + 1 day. Data for patients with an event who missed two or more scheduled assessments immediately prior to the event will be censored at the last tumor assessment prior to the missed visits.

For OS, patients who are not reported as having died will be analyzed as censored observations on the date they were last known to be alive. If no post-baseline data are available, OS will be censored at the date of randomization + 1 day.

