- irCBR is defined as the proportion of participants with irCR or irPR or irSD. Participants who do not have on-study radiographic tumor re-evaluation, who received anti-tumor treatment other than the study medication prior to reaching an irCR or irPR or irSD, or who died, progressed, or dropped out for any reason prior to reaching an irCR or irPR or irSD will be counted as non-responders in the assessment of irCBR.
- irPFS: is defined as the period from the date of treatment initiation to the date of the first documentation of objective progression of disease (irPD) or death due to any cause in absence of documented irPD. Confirmation of progression is recommended minimum 4 weeks after the first irPD assessment. Participants lacking an evaluation of tumor response after treatment initiation will have their PFS time censored on the date of treatment initiation with the duration of a day. Participants with documentation of irPD or death after a long interval (2 or more incomplete or non-evaluable assessments) since the last tumor assessment will be censored at the time of last objective assessment that did not show PD. The length of irPFS will be calculated as irPFS time (months) = [(progression, death date or censor date) – treatment initiation date +1]/30.4.
- 6-months PFS rate is defined as the proportion of patients who are alive and progression-free at 6 months from the date of first dose of study treatment based on irRECIST criteria.

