Secondary 7	FAS set	OS	
 - Patients who are not reported as having died will be analyzed as censored observations on the date they were last known to be alive. - If no post-baseline tumor assessment is available, patients will be censored at the date of treatment initiation + 1 day. 	Kaplan-Meier plot, number and proportion of events, median survival time, 1- and 2-year survival rates with corresponding 95% CI.
Sensitivity to secondary 7	PP set	OS	Same as above	Same as above
Secondary 8	FAS set	TTR	
 - Patients with no response will be censored at the date of their last evaluable imaging previous 35 days after last dose administration date. 	Kaplan-Meier plot, number and proportion of events, median survival time, 1- and 2-year survival rates with corresponding 95% CI.
Sensitivity to secondary 8	PP set	TTR	Same as above	Same as above
Secondary 9	FAS patients with overall response	DoR	
 - Patients with no progression or death will be censored at the date of their last evaluable imaging previous 35 days after last dose administration date. - If no post-response tumor assessment is available, patients will be censored at the date of treatment response + 1 day. - Data for patients with an event who missed two or more scheduled assessments immediately prior to the event will be censored at the last tumor assessment prior to the missed visits. 	Kaplan-Meier plot, number and proportion of events, median survival time, 1- and 2-year survival rates with corresponding 95% CI.
Sensitivity to secondary 9	PP patients with overall response	DoR	Same as above	Same as above
Secondary 11	FAS set	Maximum Tumor Shrinkage	Only observed cases will be used	Median, range, mean, standard deviation, and interquartile range. Waterfall plots describing the percentage of change in target tumor lesions
Sensitivity to secondary 11	PP set	Maximum Tumor Shrinkage	Same as above	Same as above

Estimand	Population	Variable	Intercurrent event strategy	Summary measure

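### The OS row of SAP Table 2 censors at day +1 when a tumor scan is missing, contradicting the SAP's own OS definition and misstating survival whenever it applies

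*SAP*

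**What the plan says.** The SAP gives three censoring statements for OS.

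- Section 5.4.1.1 defines OS as time from first dose to death from any cause, and adds: "Patients with no death will be censored on the last available follow-up date".
- Section 5.4.4, Table 2, OS row (Secondary 7), first bullet: "Patients who are not reported as having died will be analyzed as censored observations on the date they were last known to be alive".
- The same row, second bullet: "If no post-baseline tumor assessment is available, patients will be censored at the date of treatment initiation + 1 day".

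The second bullet is identical to one in the PFS row (Secondary 1) and one in the irPFS row (Secondary 12).

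Protocol section 8.6 has a day +1 rule for OS with a different trigger: "If no post-baseline data are available, OS will be censored at the date of randomization + 1 day". SAP section 5.7, which lists departures from the protocol, does not mention OS censoring. The SAP cites protocol version 1.1, whose wording cannot be checked here, but the conflict inside the SAP does not depend on it.

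Survival information does not come from scans. Protocol section 3.2.4 states that after treatment ends "survival and new anti-cancer therapy information will be collected every 3 months", and telephone contact is acceptable.

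**The concern.** A missing scan says nothing about whether a patient is alive or when he died, so it cannot be a sound trigger for censoring OS. Affected patients can arise by design. The full analysis set requires only one dose (SAP section 4), the first post-baseline scan is due at week 8 (protocol 6.4.1), and survival is followed separately. A patient can therefore have a known death date, or months of known survival, and no scan.

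The programmer has to choose between conflicting rules, and the choice moves the estimate in opposite directions. One reading removes early deaths and raises OS. The other discards follow-up and lowers it. With 18 patients and no control arm, the 1- and 2-year survival rates will be read at face value, and one or two recoded patients visibly change them. Because the trial is open-label, a choice left until analysis would be made with outcomes in view.

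**Working it through.** **The plan's own figures.** The documents give no OS sample size, event count or power. The ORR design reproduces: at least 3 responders of 16 gives exact one-sided alpha 0.043 at a 5% response rate and power 0.803 at 25%, and 16/(1 − 0.10) = 17.8, rounded up to 18. The OS rule does not touch it.

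**The rules side by side.**

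| Patient with no post-baseline scan | SAP 5.4.1.1 and first Table 2 bullet | Second Table 2 bullet, literal | Second bullet, living patients only |
|---|---|---|---|
| Died before week 8 | Event on date of death | Censored at day +1 | Event on date of death |
| Known alive from survival follow-up | Censored when last known alive | Censored at day +1 | Censored at day +1 |

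Neither reading of the second bullet agrees with the definition in both rows.

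**Fixed example.** Assume 18 patients, 9 deaths by month 12, and the other 9 followed beyond month 12. The correct 12-month Kaplan-Meier estimate is 9/18 = 50.0%. A patient censored at day +1 leaves the risk set before any event.

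- Recoding k unscanned deaths gives 9/(18 − k): 9/17 = 52.9%, 9/16 = 56.3%, 9/15 = 60.0% for k = 1, 2, 3.
- Cutting back k unscanned survivors gives (9 − k)/(18 − k): 8/17 = 47.1%, 7/16 = 43.8% for k = 1, 2.

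SAP 5.4.4 also plans exponential maximum likelihood, where the hazard is deaths divided by person-time. Recoding one of 9 early deaths cuts the numerator by 1/9, or 11%, and barely changes the denominator.

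**How many deaths could precede the first scan.** Protocol section 1.8 says only that OS is under one year, so medians of 6, 9 and 12 months are assumed. Week 8 is 56/30.4 = 1.84 months. With a constant hazard the expected number is 18 × (1 − 2^(−1.84/median)) = 3.45, 2.38 and 1.82.

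**Simulation of the literal reading.** There were 4,000 trials of 18 patients per scenario, with administrative censoring uniform between 12 and 24 months. Deaths before day 56 without a scan were recoded as censored at day 1. In the milder cases the hazard over the first 84 days is a fraction of the constant hazard, to reflect the 12-week life-expectancy criterion, and the later hazard is raised to keep the median fixed.

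| Scenario | Rise in 12-month OS, points (median 6 / 9 / 12 months) | Rise in median OS |
|---|---|---|
| Constant hazard, no early death scanned | 6.0 / 6.0 / 5.6 | about 2 months |
| Early hazard halved, half of early deaths scanned | 1.0 / 1.3 / 1.3 | 0.4 to 0.6 months |
| Early hazard quartered, half scanned | 0.4 / 0.7 / 0.7 | not summarized |

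**Simulation of the living-only reading.** If 10% to 20% of patients are unscanned for reasons other than early death (assumed), 12-month OS falls by about 1 to 4 points. At a 12-month median, for example, it falls from 50.0% to 48.1% with 10% unscanned and from 50.2% to 46.4% with 20%.

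**PFS and irPFS.** No PFS bias is claimed. The censoring table in SAP 5.4.1.1 has a line for "Death before first progression disease (PD) assessment" and counts it as an event on the date of death; the day +1 bullet in Table 2 simply fails to say so. For irPFS the tension lies inside SAP 5.4.1.2. The definition counts "death due to any cause in absence of documented irPD" as an event, and then says "Participants lacking an evaluation of tumor response after treatment initiation will have their PFS time censored on the date of treatment initiation" without excepting patients who died. The Table 2 row repeats that rule.

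**The case against.** The strongest reply is that SAP 5.4.1.1 already settles the matter: OS runs to death from any cause and only patients without a death are censored. If that section is trusted to protect PFS from the identical bullet, it should protect OS too. The literal reading would then fall away, and the 0.4 to 6 point range with it. But for PFS the SAP has an explicit line covering death before the first assessment; for OS it has only a general definition, which a more specific estimand row contradicts. Nothing gives one section precedence. Nor is the bullet an unmistakable slip: SAP 1.4 adds OS to the endpoints whose tumor response is based on RECIST, whereas the matching sentence in protocol 3.1 does not. Letting 5.4.1.1 govern deaths would still leave unscanned survivors cut back by the second bullet.

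A second reply is that the bullet is only a fallback for patients with no later date known. That would give correct OS, but it replaces the stated trigger (no tumor assessment) with another (no data), which is the correction needed.

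Other points stand. The rule does no harm if every patient is scanned, or if unscanned patients also have no survival contact. The top of the range needs a constant hazard and no scan in anyone dying before week 8, although entry requires ECOG 0-1 and a life expectancy of at least 12 weeks, and earlier scans are allowed. The exact 95% interval for 9/18 is 26% to 74%, so the shifts are small against sampling error. OS is secondary and descriptive.

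**Conclusion.** The concern holds. The OS row contradicts the SAP's own OS definition and the bullet above it, and uses a different trigger from the supplied protocol. Whenever the rule takes effect on a patient with known survival or a known death, it misstates OS: upward if early deaths are censored, downward if survivors lose follow-up. Applied literally to a mix of both, the net direction depends on the mix.

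The size depends on how many patients lack a scan, which the documents cannot tell us. One recoded patient moves a 50% 12-month rate by about 3 points. The simulated range of about 0.4 to 6 points for the literal reading rests on assumed medians of 6 to 12 months, assumed early hazards and assumed scan coverage of early deaths. The effect is confined to descriptive endpoints. It should be corrected before the analysis but threatens no primary conclusion.

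**What to change.** In the OS row of Table 2, replace the second bullet with three statements:

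1. Death from any cause is an event on its date, whether or not a scan was done.
2. Patients not reported dead are censored at the date last known alive.
3. Censoring at treatment initiation + 1 day applies only to patients not reported dead who have no post-baseline data of any kind.

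In the PFS and irPFS rows, and in the matching sentence of SAP 5.4.1.2, limit the day +1 rule to patients with neither a post-baseline scan nor an event. PFS then agrees with the censoring table in 5.4.1.1, and irPFS with its own definition.

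The cost is a few lines of SAP wording, with no new data, patients or procedures. OS may come out slightly less favorable than under the literal reading.
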